The standard practice for RCTs will be followed and a linear mixed effects model will be applied, with random intercepts to estimate the effects of treatment, time, with interaction terms for treatment (AG treatment) and time (6 and 12 weeks). The inference of interest for the study concerns the interaction term at week 12.

Assuming correlation coefficients equal to $r_{0_6_weeks} = 0.71$, $r_{0_12_weeks} = 0.65$ and $r_{6_12_weeks} = 0.69$ for the 0-6, 0-12 and 6-12 week intercorrelations, respectively, in the primary outcome values (PHQ-9), with a standard deviation of 5.60 at week 12 (numbers drawn from the results of the NCT06361667 trial) and a Cohen's d for the interaction term that is equal to 0.258 at week 12 for PHQ-9, at a type I error set at 5%, 205 participants per intervention arm would be needed for the achievement of 80% statistical power; importantly, assuming an anticipated 20% loss at follow-up rate, the total number required is 410/0.8, yielding 512 participants (256 participants by treatment arm). The power calculation was performed using the GLIMMMPSE online statistical software (<https://glimmpse.samplesizeshop.org/>)

Sensitivity analyses will be carried out, including site as a fixed/random effects factor in the models. In case of missing longitudinal data, sensitivity analyses will be performed using maximum likelihood / Last Observation Carried Forward (LOCF) approaches.

Conditions

Mental Health Issue; Anxiety Disorders; Affective Disorders; Affective Disorders, Psychotic; Psychotic disorder; Adjustment Disorder; Autism Spectrum Disorder; Mild Cognitive Impairment; Depression Disorders; Schizophrenia Disorders

Keywords

Mental Health Issue; Anxiety Disorders; Affective Disorders; Affective Psychotic Disorders; Psychotic disorders; Adjustment Disorders; Autism Spectrum Disorders; Mild Cognitive Impairment; Depression; Schizophrenia; Non-affective psychotic disorders; Psychological and behavioural factors associated with disorders or diseases classified elsewhere (ICD-10 diagnosis code F54

Primary Purpose: Other

Study Phase: N/A

Interventional Study Model: Parallel

Number of Arms: 2

Masking: None (Open Label)

Allocation: Randomized

Enrollment – Number of Participants: 512

Type: Anticipated

Arms and Interventions

Arms	Intervention

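### A random-intercept-only primary model, fitted in the usual way, probably makes the week-12 standard error slightly too small under the protocol's own planning correlations

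*Protocol*

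**What the plan says.** Everything relevant stands in the protocol under the heading on the statistical analysis model and sample size calculation.

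- **Model.** "a linear mixed effects model will be applied, with random intercepts to estimate the effects of treatment, time", with treatment-by-time interactions at 6 and 12 weeks. No residual covariance, random slope or robust standard error is mentioned.
- **Target.** "The inference of interest for the study concerns the interaction term at week 12".
- **Planning inputs.** Three different values, 0.71, 0.65 and 0.69, are given "for the 0-6, 0-12 and 6-12 week intercorrelations, respectively, in the primary outcome values (PHQ-9"), together "with a standard deviation of 5.60 at week 12". They are said to come from the earlier trial. SDs at baseline (T0) and week 6 (T1) are not given.
- **Effect and size.** "a Cohen's d for the interaction term that is equal to 0.258 at week 12 for PHQ-9", with a 5% type I error; "205 participants per intervention arm would be needed for the achievement of 80% statistical power", raised to 512 in total for 20% loss.
- **Sensitivity analyses.** These cover site effects and missing data, not the covariance structure.

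**The concern.** A random intercept with independent residuals implies compound symmetry: equal variances and one correlation for every pair of visits. A fit to data with the three planning correlations settles on roughly their average. The model then uses that average for the standard error of every contrast, including the change from baseline to week 12, where the planning correlation is lowest and the change therefore most variable.

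At stake is the width of the primary confidence interval and whether the primary test keeps its stated 5%. With dropout there is a second, smaller effect. The assumed covariance also decides how much weight a participant's T0 and T1 scores receive when the week-12 score is missing.

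**Working it through.** **Inputs.** From the protocol: r(0,6) = 0.71, r(0,12) = 0.65, r(6,12) = 0.69; SD 5.60 at week 12; d = 0.258; 205 per arm; 20% loss. Assumed: two-sided test, independent residuals, model-based standard errors and, to begin with, SD 5.60 at T0 and T1 as well.

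**The plan's own sample size.** A one-degree-of-freedom test of the week-12 change, with variance factor 2(1 − 0.65) = 0.70, needs 166 per arm; a comparison of week-12 scores alone needs 236. Neither is 205. A two-degree-of-freedom interaction test using all three correlations gives 204 per arm, and 80.2% power at 205, if the week-6 effect is taken as half the week-12 effect. That half is an assumption; the protocol gives no week-6 effect. The loss adjustment is 410/0.8 = 512.5, against 512 stated. The point below does not depend on how 205 was reached.

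**Variance of change for each visit pair, in units of SD².** Formula: 2(1 − r).

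| Pair | r | 2(1 − r) |
|---|---|---|
| 0-6 | 0.71 | 0.58 |
| 0-12 | 0.65 | 0.70 |
| 6-12 | 0.69 | 0.62 |

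**What the random-intercept model uses.** With complete data the week-12 interaction estimate is the difference in mean change under either covariance, so only the standard error differs. The model's variance for that contrast is the mean of the three rows: (0.58 + 0.70 + 0.62)/3 = 0.633, a common correlation of 0.683. The value implied by the planning figures is 0.70.

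- Standard-error ratio: √(0.633/0.70) = 0.951.
- Reported SE at 205 per arm: 5.60 × √(2 × 0.633/205) = 0.440.
- SE implied by the inputs: 5.60 × √(2 × 0.70/205) = 0.463.
- 95% half-widths: 1.96 × 0.440 = 0.86 and 1.96 × 0.463 = 0.91 PHQ-9 points.
- Actual type I error: 2 × [1 − Φ(1.96 × 0.951)] = 6.2%.

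**Simulation.** With complete data at 205 per arm, 20,000 runs gave 6.2% for the common-correlation variance and 5.1% for the contrast-specific variance. A separate REML fit of the random-intercept model (6,000 runs, Monte Carlo error about 0.3 points) gave 6.7%. With 256 per arm and 20% random loss under three assumed timings, it gave 6.1% to 6.4%.

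**The unstated SDs.** The same calculation, week-12 SD held at 5.60:

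| T0 SD | T1 SD | SE ratio | Type I error |
|---|---|---|---|
| 5.6 | 5.6 | 0.951 | 6.2% |
| 5.0 | 5.6 | 0.967 | 5.8% |
| 5.6 | 6.2 | 0.988 | 5.3% |
| 5.6 | 5.0 | 0.924 | 7.0% |
| 6.2 | 5.0 | 0.914 | 7.3% |
| 5.0 | 6.0 | 0.996 | 5.1% |
| 5.0 | 6.2 | 1.012 | 4.7% |

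Over the joint range 5.0-6.2 the error runs from 4.7% to 7.3%. It drops below 5% only where the T0 SD is low and the T1 SD high.

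**Weights when week 12 is missing (equal SDs).** Regressing week 12 on T0 and T1 under a common correlation gives 0.683/(1 + 0.683) = 0.41 for each. The three stated correlations give (0.65 − 0.71 × 0.69)/(1 − 0.71²) = 0.32 for T0 and (0.69 − 0.71 × 0.65)/(1 − 0.71²) = 0.46 for T1.

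**The case against.** **The protocol does not state independent residuals.** It names random intercepts and is silent on residual covariance and standard-error method, details often left to a SAP that is not shown. A SAP could add robust standard errors, and the problem would largely vanish. This stands as a condition on the result. It does not remove the point: the protocol positively names a structure which, as ordinarily fitted, sits badly with its own inputs. With three visits, an unstructured residual covariance cannot simply be added to a random intercept, because the intercept variance is then not separately identifiable. The wording itself would have to change.

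**The correlations are estimates.** A reader might take 0.65 as the true 0-12 correlation and conclude that the model contradicts the plan. The documents do not support that. The figures come from an earlier, smaller trial whose size is not given. If all correlations were truly 0.683, a gap between the 0-12 value and the mean at least as large as the 0.033 seen would arise by chance in roughly 30% of samples of 100, 13% of 200 and 7% of 300 (sizes assumed). Nor does entering three correlations in a power calculation oblige the analysis to use the same structure.

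**The direction is not certain.** A reader might infer that type I error always exceeds 5%. That holds when one SD at a time is varied over 5.0-6.2 (5.3% to 7.0%), but not when both vary.

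**The consequence is small.** This stands: 0.05 points of half-width on a 0-27 scale. No bias from the dropout weights has been shown.

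**Conclusion.** The concern holds in a conditional and modest form. With independent residuals, model-based standard errors, the planning correlations taken at face value and equal SDs at the three visits, the week-12 interaction standard error is about 5% too small and the nominal 5% test runs at about 6.2%. Only the week-12 SD is documented; across plausible T0 and T1 SDs the error lies between about 4.7% and 7.3%, usually but not always above 5%. With complete data the treatment estimate is untouched.

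This does not show that the trial's result would be invalid or that the test must be anticonservative. It shows that the named model protects the primary error rate less well than an alternative that costs almost nothing. The change is worth making before analysis.

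**What to change.** In the statistical analysis section, replace the random-intercept clause with a repeated-measures mixed model that has visit as a factor and an unstructured within-participant covariance over T0, T1 and T2, fitted by REML. Alternatively, keep the random intercept and state that participant-level robust standard errors will be used. That corrects the standard error but leaves the dropout weights as they are.

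The cost is one sentence. The unstructured model has six covariance parameters instead of two, negligible with about 512 participants. Under the planning figures the primary interval becomes about 5% wider (0.463/0.440 = 1.05). No extra patients are needed: at 205 per arm the week-12 contrast has 87.7% power with variance factor 0.70, reading d = 0.258 in outcome-SD units.

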This trial will be conducted as part of the novel Arts on Prescription initiative of the Hellenic Ministry of Culture in Greece and at several Ministry-of-Culture-approved Organisations from the field of arts and culture. The University Mental Health, Neurosciences and Precision Medicine Research Institute 'COSTAS STEFANIS' (UMHRI) was commissioned by the Ministry of Culture to organize and conduct the RCT. In the beginning, an open invitation to institutions of culture and mental health has been sent. Cultural organizations presented their action plans for interventional courses. After quality control by the UMHRI and the Ministry of Culture. the following cultural organizations provided approved action plans: National Gallery - Alexandros Soutsos Museum, National Museum of Contemporary Art Athens, Athens Concert Hall Organization, Greek National Opera, Athens Conservatoire, Michael Cacoyannis Foundation, Stavros Niarchos Foundation Cultural Center (SNFCC), Nikolaos and Dolly Goulandris Foundation - Museum of Cycladic Art, Galilee Palliative Care Centre of the Holy Metropolis of Mesogaia and Lavreotiki, Archaeological Museum of Thessaloniki, Thessaloniki Concert Hall Organization, Metropolitan Organisation of Museums of Visual Arts of Thessaloniki (MOMus)", Kazantzakis Museum, Paul and Alexandra Canellopoulos Museum, National School of Dance (KSOT), Municipal Regional Theatre of Ioannina, National Theatre of Northern Greece, Drama International Short Film Festival (DISFF) Cultural Organization, and Heraklion Archaeological Museum.

AG consists of art intervention sessions that have been *a priori* developed by each cultural organization, specific to the field of each cultural organization (i.e., theatre, dance, visual arts, music, cinema). The intervention sessions have been elaborated and enhanced based on the previous experience of the NCT06361667 trial; specifically, the differences versus the NCT06361667 trial are the following: i. all Cultural Organizations are offering weekly sessions and there is no variability in the total number of sessions provided, ii. a larger sample is included in this trial to improve the precision of estimates and be able to detect smaller effect sizes (given the potential scalability and public health relevance of

the intervention, and iii. this trial includes Cultural Organizations and therefore patients beyond the metropolitan areas of Athens and Thessaloniki.

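### Does the sample size of 205 per arm fail to follow from the protocol's printed inputs for the week-12 interaction?

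*Protocol*

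**What the plan says.** All of the following is in the Protocol, under the heading on the statistical analysis model and sample size calculation, unless stated otherwise.

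- Analysis: "a linear mixed effects model will be applied, with random intercepts to estimate the effects of treatment, time", with treatment-by-time terms at 6 and 12 weeks.
- Target of inference: "The inference of interest for the study concerns the interaction term at week 12". This is a single contrast, the between-arm difference in change from baseline to week 12.
- Planning inputs: correlations of 0.71 (weeks 0 and 6), 0.65 (0 and 12) and 0.69 (6 and 12); "with a standard deviation of 5.60 at week 12 (numbers drawn from the results of the NCT06361667 trial"; a Cohen's "d for the interaction term that is equal to 0.258 at week 12 for PHQ-9"; type I error 5%.
- Result: "205 participants per intervention arm would be needed for the achievement of 80% statistical power", raised for 20% loss to 512 in total, 256 per arm.
- Software: "The power calculation was performed using the GLIMMMPSE online statistical software".

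The Detailed Description gives the reason for the size: "a larger sample is included in this trial to improve the precision of estimates and be able to detect smaller effect sizes".

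Not printed are the SD at baseline or week 6, an effect at week 6, the SD that scales d, whether the test is two-sided, and the hypothesis entered in the software.

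**The concern.** The section lists inputs, states a sample size as their consequence, and names one test. A reader who takes 5.60 as the common SD and runs that test gets 167 per arm, not 205. A gap of 38 per arm is too large for rounding or for a t rather than a normal reference.

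This is the protocol's only power statement and it fixes enrolment. The larger sample is justified by the wish to detect smaller effects, so the detectable effect matters to the rationale. On the common-SD reading, 205 per arm detects about 1.30 PHQ-9 points (d = 0.232) rather than 1.44 points (d = 0.258). A further worry is that the software may have powered a joint test of both interaction terms instead of the declared week-12 term.

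**Working it through.** **The plan's own figures.** The loss adjustment reproduces: 2 × 205 = 410, and 410/0.8 = 512.5, printed as 512. The half participant is immaterial. The step to check is 205.

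**Inputs from the protocol.** r(0,12) = 0.65; SD at week 12 = 5.60; d = 0.258; alpha 5%; power 80%; equal arms. **Assumed:** a two-sided test and the baseline SD, s0.

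**Formulas.** SD of change = √(s0² + 5.60² − 2 × 0.65 × s0 × 5.60). To a normal approximation, n per arm = 2 × (1.960 + 0.842)² × (SD of change / difference)². The results below use the noncentral t, which adds one or two per arm.

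**Reading 1: d scaled by 5.60, s0 = 5.60.** Difference = 0.258 × 5.60 = 1.445 points. SD of change = 5.60 × √(2 × 0.35) = 4.685. The normal approximation gives 2 × 7.849 × (4.685/1.445)² ≈ 165.1, so 166. The t-based figure is 167. Power at 205 per arm is 87.6%, and the difference detectable with 80% power is 1.300 points, or d = 1.300/5.60 = 0.232.

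**Reading 2: d scaled by 5.60, other baseline SDs.** These SDs are assumptions, because the protocol prints none.

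| Assumed baseline SD | SD of change | n per arm for 80% | Power at 205 |
|---|---|---|---|
| 5.0 | 4.468 | 152 | 90.4% |
| 5.6 | 4.685 | 167 | 87.6% |
| 6.0 | 4.866 | 180 | 85.1% |
| 6.4 | 5.072 | 195 | 82.0% |
| 6.64 | 5.207 | 205 | 80.0% |
| 6.8 | 5.301 | 213 | 78.6% |

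A baseline SD of 6.64, which is 1.04 points above the week-12 value, returns the protocol's figure for the declared test.

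**Reading 3: d scaled by the SD of change.** The standardised difference in change is then 0.258 itself. The normal approximation gives 2 × 7.849/0.258² ≈ 235.8, so 236. The t-based figure is 237, and power at 205 is 74.1%.

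**Reading 4: a joint two-degree-of-freedom test of both interaction terms**, using the three printed correlations, equal SDs and an assumed week-6 effect. Expressed as a fraction of the week-12 effect, 0 gives 150 per arm, 0.25 gives 189, 0.5 gives 204, 0.75 gives 182 and 1 gives 141. A fraction of about one half comes within one participant of 205 (power 80.2% at 205).

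**What this shows.** Readings 1 to 3 all concern the declared week-12 test, and they differ only in inputs the protocol leaves unprinted. Across them, power at 205 runs from 74.1% to 90.4%, on both sides of 80%. Two separate routes, a larger baseline SD (Reading 2) or a joint test (Reading 4), return 205 or 204. The document does not say which was used, if either.

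**The case for a change.** The strongest case for a change is that the protocol did not defer this calculation: it printed inputs and stated a result, and with equal SDs no standard two-sided version of the week-12 test gives 205. Random intercepts, as described, imply the same variance at every visit, so a common 5.60 is the natural reading. The joint test with a half-sized week-6 effect fits closely and uses all three correlations, two of which the week-12 change contrast does not need. If that test was the one powered, the trial was sized for a hypothesis other than the declared one. Printing the missing inputs would take one or two sentences.

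Part of this stands: from the protocol alone a reader cannot reproduce 205 or state the detectable effect for the week-12 contrast.

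The rest does not carry. The protocol ties 5.60 to week 12, which points to SDs that differ by visit. The equal-variance argument is selective, because random intercepts also imply a single correlation and the protocol prints three unequal ones; the planning covariance was plainly not taken from that model. The joint-test explanation is conjecture: it needs a week-6 effect stated nowhere, and a larger baseline SD explains 205 equally well under the declared test.

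**Conclusion.** No change to the plan follows. The week-12 contrast cannot be computed from the printed inputs without assuming a baseline SD and a scale for d, so the mismatch reflects incomplete reporting, not a demonstrated error. Assuming a two-sided 5% test, 205 per arm gives 87.6% power if 5.60 is both the common SD and the scale of d, 80.0% if the baseline SD is 6.64, and 74.1% if d is scaled by the SD of change. These figures neither refute the stated 80% nor show the trial to be underpowered.

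The missing inputs are of the kind often held in an SAP or power report, and the SAP is not available here. Even on the critical reading, the 512 participants, the PHQ-9 endpoint, the mixed model and the week-12 inference would all remain, so a trial run as written yields the same estimate with the same precision. If the result is null, the confidence interval for the week-12 difference will show which effects are excluded, whatever planning SD was used.

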Participants will be randomly allocated to AG or WL for 12 weeks; that marks the end of the trial period. After completion of the 12-week trial, people who were included in the WL will have the opportunity to receive art on prescription by the Cultural Organizations the participated in the trial, should they wish to take this up.

Randomisation will be performed separately in each Cultural Organization and will be carried out using a computer-generated list provided centrally by SIBA Soft (Athens, Greece), an independent software and project management company.

Frequency of Measurement:

Data will be collected at baseline, including gender, age, educational level, marital status, socioeconomic characteristics, and mental health conditions. The primary and the secondary outcomes will be measured at time points:

- T0: (before the randomisation; and after informed consent and patient's sociodemographic data)
- T1: 6 weeks (after the start of the intervention for the AG group or the entry into the study for the WL group)
- T2: 12 weeks (after the start of the intervention for the AG group or the entry into the study for the WL group)

Interventional Model Description:

The duration of the RCT will be 12 weeks. The AG group will engage in different art forms (theatre, dance, visual arts, music, and cinema), whereas the WL group will remain in the waiting list.

The AG intervention will consist of sessions and/or performances in one of the five art forms: theatre, dance, visual arts, music and cinema. The number of sessions/performances will be 12 for all art forms over the duration of the trial, based on the specific features of each Cultural Organization.

The intervention activities in the AG group have been organized by each site and approved by the UMHRI and the Hellenic Ministry of Culture creating a space for 8-16 participants per activity.

The intervention consists of weekly visits over three months, featuring a guided tour followed by an art activity. All activities will include a discussion group, fostering reflection and connection, and each session will last approximately 1.5 to 2 hours. UMHRI and Ministry of Culture-approved, experienced professionals from the fields of mental health and arts, will lead the intervention sessions ensuring the safety and support of participants.

Statistical analysis model and sample size calculation

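### Site defines the randomisation but is left out of the primary model; this touches the week-12 test only if sites differ in change over time, and with balanced lists it then makes the test conservative

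*Protocol*

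**What the plan says.** In the Detailed description of the Protocol, just before Frequency of Measurement: "Randomisation will be performed separately in each Cultural Organization and will be carried out using a computer-generated list provided centrally". The Design text lists 19 organizations with approved plans and notes that "this trial includes Cultural Organizations and therefore patients beyond the metropolitan areas of Athens and Thessaloniki".

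Under Statistical analysis model and sample size calculation, the primary analysis is fixed as follows: "a linear mixed effects model will be applied, with random intercepts to estimate the effects of treatment, time, with interaction terms" of treatment and time. The target is explicit: "The inference of interest for the study concerns the interaction term at week 12". Site comes in only later: "Sensitivity analyses will be carried out, including site as a fixed/random effects factor in the models".

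The protocol does not say whether the lists are blocked, at which level the random intercept sits (participant is the natural reading, since site is reserved for sensitivity analyses), or whether the site factor is an intercept only or also varies by visit.

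**The concern.** The factor that structures the randomisation would normally be carried in the primary analysis, so that the reported standard error (SE) reflects the variance that the allocation produces. Here the protocol assigns it to a sensitivity analysis. That is a stated choice, not a gap that an unseen SAP might fill.

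There is some reason to expect sites to differ in change. Each organization developed its own sessions, the art forms differ, and recruitment now reaches beyond two cities; this last point concerns both arms. At stake is the calibration of the week-12 test, and possibly some precision. The sensitivity analysis itself is also in question: if it adds only a site intercept, it can say little about the contrast it is meant to protect.

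**Working it through.** **Inputs from the protocol.** SD 5.60 at week 12 (variance 31.36); correlations 0.71 (0-6 weeks), 0.65 (0-12) and 0.69 (6-12); d = 0.258; 205 per arm; 20% loss; 19 organizations, counted from the list.

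**Assumptions.** SD 5.60 at every visit; two-sided 5% test; 1:1 allocation in every organization (consistent with 256 per arm); 19 × 22 = 418 participants, 209 per arm, close to the 410 completers. Let s be the share of PHQ-9 variance that is a site-by-visit effect, common to both arms and independent between visits, with s = 0 / 2 / 5%.

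**1. The plan's own figure.** A 2-df treatment-by-time test with a linear effect (0, d/2, d) gives 204 per arm, and 80.2% power at 205, so the stated 205 is reproduced. The single week-12 change contrast gives 2 × (1.960 + 0.842)² × 2(1 − 0.65) / 0.258² = 165.1, so 166. Neither calculation contains a site term.

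**2. Constant site effects.** The week-12 interaction compares within-participant changes. A site effect that is the same at each visit drops out of week 12 minus baseline. In simulation with complete data, adding a site intercept gave a shift in the estimate of 0.0000 and an SE ratio of 1.0000. With 20% dropout (3,200 runs over 8 settings), the 95th percentile of the absolute shift was 0.036-0.060 points, the largest was 0.103, and SE ratios were 0.994-1.002.

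**3. What s means for change.** Change variance is 2 × 31.36 × (1 − 0.65) = 21.95. The site part is 2 × s × 31.36 = 0 / 1.25 / 3.14, that is 0 / 5.7 / 14.3% of change variance. The between-site SD in 12-week change is 0 / 1.12 / 1.77 points.

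**4. Balanced lists, covariance correct.**
- True SE = √[2 × (21.95 − 2 × s × 31.36) / 209] = 0.458 / 0.445 / 0.424. It is the same whether or not site is fitted.
- Reported SE without site, unstructured covariance = √(2 × 21.95 / 209) = 0.458 at every s.
- Ratio of reported to true: 1.00 / 1.03 / 1.08.
- Type I error = 2 × P(Z > 1.96 × ratio) = 5.0 / 4.4 / 3.4%. Simulation (12,000 runs per cell, error about 0.2 percentage points) gave 4.8 / 4.5 / 3.7%.

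**5. Unrestricted lists.** Without site, the true SE is about 0.458 at every s, which is also the unstructured reported SE. With site-by-visit terms, the expected information is 19 × (22 − 1) / 4 = 99.75, so SE = √[(21.95 − 2 × s × 31.36) / 99.75] = 0.469 / 0.456 / 0.434. The change is about +2 / −1 / −5%, in line with simulated SEs of 0.467 / 0.455 / 0.434 against 0.456 / 0.459 / 0.458.

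**6. The separate covariance issue.** A random intercept implies one common correlation, (0.71 + 0.65 + 0.69) / 3 = 0.683. Reported SE = √[4 × 31.36 × (1 − 0.683) / 209] = 0.436. Against 0.458 the ratio is 0.951, so type I error is 6.2% at s = 0, with no site effect at all.

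**7. Models side by side (balanced lists, s = 0 / 2 / 5%).**

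| Model | Reported SE | Type I error |
|---|---|---|
| Random intercept, no site (as planned) | 0.436 / 0.436 / 0.436 | 6.2 / 5.5 / 4.4% |
| Random intercept + site-by-visit | 0.436 / 0.422 / 0.400 | 6.2 / 6.3 / 6.5% |
| Unstructured, no site | 0.458 / 0.458 / 0.458 | 5.0 / 4.4 / 3.4% |
| Unstructured + site-by-visit | 0.458 / 0.445 / 0.424 | 4.8 / 5.3 / 5.2% (simulated) |

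**The case against.** A reader might infer from the mismatch that leaving site out biases the estimate or inflates false positives. The documents do not support either. With a common allocation ratio the comparison is unbiased with or without site. The 6.2% arises with no site effect at all, so it belongs to the covariance structure and not to site. Nor can one say without conditions that the SE and test size fail to follow the randomisation: blocking is not stated, and with unrestricted lists omitting site leaves the size of a test with correct covariance essentially at its nominal level.

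The strongest case for the sponsor goes further, and much of it stands:
- Taken alone, the omission is harmless or conservative.
- Moving the planned site factor into the primary model as an intercept would change nothing of note.
- Adding site-by-visit terms to the random-intercept model would raise type I error at two of the three assumed shares.
- The 5% share is demanding. It implies a between-site SD in change of 1.77 points, more than the target effect of 0.258 × 5.60 = 1.44 points, and nothing in the protocol supports a value that large.

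It can also be said that the form of the site term and the covariance are SAP matters. That is fair for those details. It does not cover the role of site, which the protocol itself fixes as sensitivity only.

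**Conclusion.** The point holds in a limited form and is minor. The randomisation stratum is absent from the primary model.

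- **Constant site differences:** no consequence with complete data, and under 1% in SE with 20% dropout. A sensitivity analysis with a site intercept alone would therefore be uninformative about the week-12 contrast.
- **Sites differing in change, balanced lists:** the reported SE is up to 3% too large at a 2% share and 8% at a 5% share, and the test is conservative. The true variance is unaffected.
- **Sites differing in change, unrestricted lists:** the issue is precision, about 5% in SE at the 5% share.

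The random-intercept covariance is a separate source of error and acts in the opposite direction. Where the planned test ends up depends on a site variance that the protocol does not give.

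All sizes rest on the assumed shares, equal SDs across visits, equal site sizes and 1:1 allocation within sites.

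**What to change.** Under Statistical analysis model and sample size calculation, define the primary model with treatment, visit, treatment-by-visit, Cultural Organization and Cultural Organization-by-visit. State in advance whether the site terms are fixed or random. Specify an unstructured covariance over the three visits, and make the model without site the sensitivity analysis. The site and covariance changes belong together, because site-by-visit terms alone would leave type I error at about 6.2-6.5%.

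The cost is analysis wording. Site is already known for every participant. Fixed site terms use 18 degrees of freedom per visit, and about 2% in SE is lost if lists are unrestricted and sites do not differ in change.

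The change does not deal with clustering in the active-arm groups, described under Interventional Model Description as "creating a space for 8-16 participants per activity". Site terms common to both arms do not repair that, and it needs its own treatment.

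### LOCF as a missing-data sensitivity analysis can produce a false PHQ-9 difference in either direction if loss differs by arm in amount or timing; a delta-adjusted analysis would be a better check

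*Protocol*

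**What the plan says.** All the statistical text is in the protocol section on the statistical analysis model and sample size calculation. For the main analysis, "a linear mixed effects model will be applied, with random intercepts", including treatment-by-time interactions at weeks 6 and 12. The target is explicit: "The inference of interest for the study concerns the interaction term at week 12". For missing longitudinal data, "sensitivity analyses will be performed using maximum likelihood / Last Observation Carried Forward (LOCF) approaches". No other missing-data analysis is named there.

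The sample size works with "with a standard deviation of 5.60 at week 12", a standardised effect of 0.258 and correlations of 0.71 (weeks 0 and 6), 0.65 (0 and 12) and 0.69 (6 and 12). It inflates 410 to 512, or 256 per arm, "assuming an anticipated 20% loss at follow-up rate". That loss is not divided by arm or by visit.

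Under Frequency of Measurement, outcomes are taken at T0, week 6 and week 12, so only the T0 or week-6 value can be carried forward to week 12. The trial is open label. For AG, "The number of sessions/performances will be 12 for all art forms over the duration of the trial"; WL receives nothing until an optional offer after week 12.

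**The concern.** LOCF replaces a missing week-12 score with an older one and treats it as observed. If mean PHQ-9 moves over the 12 weeks for reasons unrelated to treatment, each person lost contributes too little of that movement, and someone lost after T0 contributes none. When the arms lose different proportions, or lose them at different times, these shortfalls do not cancel. The sign depends on which arm leaves more or earlier, so LOCF cannot be relied on to be conservative.

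This is plausible here. Participants know their arm, AG has sessions to keep attending and WL has only a later offer to wait for. The document does not indicate which arm would lose more.

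What is at stake is the robustness statement. Agreement or disagreement between LOCF and the primary result could simply reflect who left and when.

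A smaller wording point: the estimator for the primary mixed model is not named. If it is ML or REML on all observed visits, as is usual, the maximum likelihood entry rests on the same missing-at-random assumption and adds no separate check.

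**Working it through.** **Inputs from the protocol.** SD 5.60 at week 12; correlations 0.71, 0.65 and 0.69; effect size 0.258; 20% loss; 256 per arm; type I error 5% (taken as two-sided).

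**Assumptions not in the protocol.** No true effect; the same linear change c in both arms, half of it reached by week 6; the split and timing of loss; SD 5.60 at every visit. The false difference does not depend on the SD; the rejection rates do.

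**The plan's own figures.** Planned difference: 0.258 × 5.60 = 1.4448 points. Inflation: 410/0.8 = 512.5, against 512 stated. The 205 per arm is reproduced to within one (204) by a 2-df treatment-by-time test with the week-6 effect set at half the week-12 effect. None of this is in dispute.

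**False difference.** Let p0 be the proportion lost after T0 and p6 the proportion lost after week 6; A and W denote AG and WL. With c the common improvement, the LOCF mean improvement in an arm is c[(1 − p0 − p6) + 0.5 p6] = c[1 − p0 − 0.5 p6]. The spurious advantage of AG is therefore

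c[(p0W − p0A) + 0.5(p6W − p6A)].

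For c = 2, with the larger or earlier loss in WL:

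| Loss pattern (WL / AG) | Calculation | False difference | Share of 1.44 |
|---|---|---|---|
| 20 / 20, same timing | 2 × 0 | 0 | 0% |
| 22 / 18, after week 6 or after T0 | 2 × 0.02; 2 × 0.04 | 0.04; 0.08 | 3%; 6% |
| 25 / 15, after week 6 or after T0 | 2 × 0.05; 2 × 0.10 | 0.10; 0.20 | 7%; 14% |
| 30 / 10, after week 6 or after T0 | 2 × 0.10; 2 × 0.20 | 0.20; 0.40 | 14%; 28% |
| 20 / 20, WL 15 after T0 + 5 after week 6, AG 5 + 15 | 2[0.10 − 0.05] | 0.10 | 7% |
| 20 / 20, WL all after T0, AG all after week 6 | 2[0.20 − 0.10] | 0.20 | 14% |

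Values halve for a 1-point trend and rise by half for a 3-point trend. With improving scores, more or earlier loss in WL falsely favours AG; swapping the arms, or having scores worsen, reverses the sign.

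**Rejection rates at nominal 5%, c = 2.** On LOCF-filled data every participant has three values, so the random-intercept interaction equals the difference in mean change. Its model SE is sqrt(4 s²/n), where s² is the mean variance minus the mean covariance.

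- No loss: s² = 31.36 × (1 − 0.6833) = 9.93, so the model SE is sqrt(4 × 9.93/256) = 0.394. The true SE is sqrt(4 × 31.36 × 0.35/256) = 0.414. Rejection is 6.2%; the excess over 5% comes from the equal-correlation assumption of the random-intercept model, not from LOCF.
- Equal 20% loss and timing: true/model SE 0.377/0.356 (after T0) and 0.408/0.379 (after week 6); rejection 6.4% and 6.9%. The model SE falls below 0.394, so lost data look like added precision.
- 25/15: 10.2% (after T0), 7.7% (after week 6). For the first, the critical value is 1.96 × 0.356 = 0.698; the tail beyond (0.698 − 0.20)/0.377 = 1.32 is 9.3%, and the opposite tail adds 0.9%.
- 30/10: 21.7% and 10.2%.
- Equal loss, different timing: 7.6% (15 + 5 against 5 + 15) and 10.2% (extreme).

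A change-score test, whose SE is correct, gives 5.7% to 8.3% for 25/15 and 7.8% to 18.6% for 30/10. Simulation with 4,000 runs per case agrees: for 30/10 the mean false difference is 0.398 with 22.1% rejection (T0 loss) and 0.194 with 9.8% (week-6 loss). On the same simulated trials, the random-intercept model fitted by REML to observed visits has a mean difference within 0.011 of zero and rejects 6.0% to 6.9%.

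**Tipping point for the alternative.** Shifting the imputed week-12 scores of AG dropouts by delta moves the contrast by (AG proportion lost) × delta. If the planned 1.4448 is observed with 20% loss, and the SE is treated as unchanged by the shift, significance goes when delta = (1.4448 − 1.96 × SE)/0.20. SE 0.455 (unstructured covariance, T0 loss) or 0.448 (week-6 loss) gives about 2.8. SE 0.463 (change score, 205 completers per arm) gives 2.7.

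**The case against.** The strongest reply is that nothing decisive depends on LOCF. It is a conditional sensitivity analysis with no decision rule, and in these same null scenarios the mixed model on observed visits stays essentially unbiased. That stands, and it limits the weight of the point.

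The bias also needs both a shared drift and unequal loss, and the protocol supplies neither; this is a general property of LOCF rather than a slip peculiar to this trial. That stands too. Mild cases are negligible: 22/18 loss, or a 1-point trend with 25/15 loss after week 6 (0.05 points). Rejection rates must be read against 6.2% to 6.9%, not 5%; the 7.6% timing case is only about one percentage point above that baseline.

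The maximum likelihood remark depends on an estimator that the protocol does not name. If the primary fit used complete cases only, that entry would be a real check. It is a wording point and carries no weight here.

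Finally, missing-not-at-random analyses and their grids are commonly left to the SAP, which is not available, so the lack of a tipping-point analysis is not itself a fault. Agreed. But LOCF is a method the protocol positively names, and that choice is open to comment.

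**Conclusion.** The concern holds, as an optional improvement. LOCF can create a false week-12 PHQ-9 difference of either sign when the amount or timing of loss differs by arm, even under random loss within arms. With an assumed shared 2-point improvement and no true effect, the size is 0.10 to 0.20 points for 25/15 loss or for equal loss with different timing, and up to 0.40 points, about 28% of the planned effect, in the illustrative 30/10 extreme. It is zero with no drift or with equal loss and timing. The primary inference and the sample size are untouched; what is weakened is the value of LOCF as evidence of robustness.

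**What to change.** State in the protocol that the likelihood-based mixed model on all observed visits is the missing-at-random analysis. Replace LOCF with a delta-adjusted (tipping-point) multiple-imputation analysis that shifts imputed week-12 PHQ-9 separately in AG and WL over a pre-stated grid, for example −4 to +4 points. The grid can be fixed in the SAP. It contains the 2.7 to 2.8 tipping point at 20% AG loss. If AG loss were only 10%, shifting AG alone would need about 0.553/0.10 = 5.5 points (0.553 = 1.4448 − 1.96 × 0.455, keeping the same SE), so the grid would then have to vary both arms together or be wider.

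The cost is one sentence and modest programming, with no new data and no change in sample size. The downside is a possibly less favourable robustness statement.
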